Tumor assessments will be by irRC for solid tumors, modified IWG for AML, and/or standard tumor markers as appropriate, and quantitative RT-PCR for WT1 transcript for AML. Perform every 8 weeks after first dose or more frequently as clinically indicated. Tumor markers drawn from peripheral blood samples should be assessed every 4 weeks after the first dose. This assessment may be performed ± 7 days of the scheduled assessment but must be completed before the next planned administration of study drug. For patients with AML if no other measurable disease then bone marrow aspirations/biopsies should follow the general post-transplant biopsy schedule or other clinical site guidelines. Progressive disease requires confirmation by a repeat, consecutive assessment at least 4 weeks after the date of first documentation, unless rapid clinical deterioration is seen. For patients with glioblastoma, progressive disease should additionally be confirmed by SPECT, perfusion MRI, MRI spectroscopy or C-14 methionine PET or pathology from available surgical/biopsy specimens to differentiate from pseudoprogression. For patients with AML, bone marrow aspirations/biopsies are scheduled when clinically indicated, however peripheral blood should be assessed for blasts and WT1 transcript at least every 4 weeks or more frequently as clinically indicated.

<sup>n Tumor markers drawn from peripheral blood samples should be assessed at least every 4 weeks after the first dose but may be performed more frequently (For other tumor assessments, perform every 8 weeks after first dose or more frequently as clinically indicated).

<sup>o Following the End of Study visit, patients will be contacted every 3 months to evaluate disease progression, if not already reached, and survival.

<sup>p The Consolidation Phase includes a maximum of 6 doses. Patients who do not complete the extended dosing in the Consolidation Phase for reasons other than intercurrent medical conditions may continue in the study and start dosing in the Maintenance phase as scheduled on Day 169, at the discretion of the investigator and the sponsor.

The window algorithm rules will be only applied to the unscheduled assessments. For scheduled assessments (except CA-125 that is mapped according to the schedule of tumor assessment), they will be kept as what they are recorded according to the schedule of assessments in protocol. The window algorithm is described as follows. For an unscheduled assessment, based on its relative study day with respect to the date of the first dose, map it to the nearest scheduled assessment according to Day described in the schedule of assessments in protocol. If there is already a scheduled assessment, keep this unscheduled assessment as unscheduled assessment.

# 6.2. Primary Endpoint Variables

The safety and tolerability of WT2725 Dosing Emulsion will be evaluated based on the occurrence of DLT and AEs, and the findings from clinical laboratory tests, vital signs measurements, body weight measurements, and ECG results.

The determination of the MTD of WT2725 Dosing Emulsion will be based on the incidence of DLT at each dose escalation cohort and the overall safety profile of WT2725 Dosing Emulsion. The incidence of DLT will be evaluated during the DLT Evaluation Period.

# 6.3. Secondary Endpoint Variables

- Proportion of patients in each overall response category for each dose cohort based on irRC, modified IWG, and/or tumor markers, as appropriate, for all posttreatment tumor assessments.
- Percent change in tumor burden from baseline to each posttreatment tumor assessment and the last tumor assessment for each dose cohort.
- The amount of immune response evaluated by:
  - Measurement in peripheral blood of WT1 peptide-specific Cytotoxic T lymphocyte (CTL) induction activity at each assessment time.
  - Measurement in peripheral blood of WT1 serum antibody titer at each assessment time.
  - o DTH to the WT2725 peptide at each assessment time.
  - Measurement of level of expression of CD8+, Foxp3, human leukocyte antigen (HLA) class I, and WT1 protein in tumor tissue using immunohistochemistry (IHC) methods

# 6.4. Exploratory Variables

- Correlation between the level of expression of WT1 protein and the degree of the immune response at each assessment time as measured by CTL induction.
- Evaluation of changes in activity in peripheral blood mononuclear cells (PBMCs) after administration of study drug.

# 6.5. Additional Exploratory Endpoints

Progression-free survival (PFS), time to progression (TTP) and duration of response will be summarized for solid tumor patients. Duration of Composite Complete Remission (CRc), duration of response (CRc + partial remission [PR]), and time to progression for AML (TTPAML) will be summarized for AML patients. Overall survival (OS) will be summarized for all patients and by disease category (solid tumor vs. AML).

### 6.6. Safety Assessments

Safety assessments will be conducted at each study visit as indicated on the Schedules of Assessments (Table 1 and Table 2) and will include the spontaneous reporting of AEs, physical examinations, determinations of vital signs, body weight measurements, ECGs, and clinical laboratory determinations including complete blood count, serum chemistries, and urinalysis. Careful monitoring for signs of local injection site reactions will be performed during the study.

In addition, these assessments will be used to describe the DLT and determine the MTD.

# 6.7. Drug Concentration Measurements

Not Applicable.

# 7. STATISTICAL METHODS

# 7.1. General Methodology

Continuous variables will be summarized by mean, standard deviation, 25th percentile, median (50th percentile), 75th percentile, minimum and maximum values. Categorical variables will be summarized using counts and percentage. In general, data will be summarized by enrolled or starting dose cohort. Efficacy data will also be summarized by tumor type and/or outcome measurement.

All raw data will be presented to the original number of decimal places. The means, medians, and percentiles will be presented to 1 more decimal place than the raw data. The standard deviations will be presented to 2 more decimal places than the raw data.

Due to the small sample size of the study, the Wilson Score 95% confidence interval s (CIs) will be used in the summary for the binomial proportion of the derived best overall response for both solid tumor irRC patients and the AML patients, separately. This interval is obtained using the following formula and further details are presented in

reference [Newcombe-1998]:  $(2np + z^2 + /- z\sqrt{[(z^2 + 4npq)]/2(n + z^2)})$ , where n=total sample size, p=observed probability of "success", q=1-p and z= 1-  $\alpha/2$  point of the standard Normal distribution.

The Spearman's rank correlation will be calculated for specified exploratory endpoints (or biomarkers). This will be carried out using the CORR procedure in SAS v9.1.3 or higher.

# 7.2. Adjustments for Covariates

Not applicable.

# 7.3. Handling of Dropouts or Missing Data

Missing observations will generally be treated as missing at random and will not be imputed, unless otherwise noted.

Adverse event and concomitant medication dates will be imputed as follows:

Start Date: If only 'day' is missing, and the month and year are not the same as the month and year of first dose, then impute day with '01'. Otherwise, if the month and year are the same as first dose date, use first dose date. If 'day' and 'month' are missing, and 'year' is not missing, then impute month and day with month and day of first dose date (assuming same 'year'). If the year is not the same as the year of first dose, impute 01 for day and 01 for month. If the start date is completely missing, it will be set to the first dose date.

Stop Date: If only 'day' is missing, impute day with last day of the month. If 'day' and 'month' are missing, and 'year' is not missing, then impute month with '12' and day with '31' (or date of study discontinuation/completion if earlier than 12-31). If the stop date is completely missing, it will be set to the date of study discontinuation/completion. A stop date will not be applied to ongoing AEs.

Note, for all listings the actual value for date (not imputed) will be presented in all data listings and imputed dates will only be used for programming flags, etc.

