4. AMENDMENT NO. 2, PROTOCOL VERSION 3.0 (13 JUL 2012)

The following changes were made to the protocol in order to adhere to the sponsor's internal standards:

- Revise definitions for reporting adverse events:
 - remove “unlikely” from the reasons for causal relationship of adverse events to study medication and adjust adverse event statistical analysis accordingly
- Change start time for collection of adverse events, serious adverse events, and pregnancies to the time of informed consent

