#### 8.7.2. Adverse Events

All AE tables summarized by MedDRA coding will be sorted alphabetically by SOC and decreasing incidence of preferred term within based on the total number of patients. AE summaries will be produced by dose cohort and tumor group.

Treatment-emergent adverse events (TEAEs) will be defined as:

- AEs that occurred on or after the first dose of study drug and on or before the 30th day after the last dose of study drug,
- AEs with a missing start date and a stop date on or after the first dose of study drug, or
- AEs with both a missing start and stop date.

All the following summaries of AEs, unless otherwise stated, will include only TEAEs. An overall summary of AEs, including the number and percentage of patients reporting at least 1 AE, treatment-related AEs, AEs with an outcome of death (defined as CTCAE Grade 5 or outcome is "fatal"), serious AE (SAE)s, treatment-related SAEs, and AEs leading to treatment discontinuation (defined as an event with an outcome code of "drug withdrawn").

Tables will present the number and percentage of AEs by starting dose cohort and overall and by MedDRA SOC and PT for the Safety population. The following tables will be produced:

- TEAEs (including number of events and patient incidence)
- Treatment-Related TEAEs. "Related" is defined as all responses other than "Unrelated" from the CRF. If a patient reports more than one AE within the same treatment regimen, SOC and PT, and any are related, it will be summarized as related. If in CRF, no choice is ticked, it will be treated as "Related".
- SAEs
- Treatment-Related SAEs
- TEAEs by maximum CTCAE Grade
- TEAEs leading to treatment discontinuation
- TEAEs with outcome of death

Similar tables will also be presented by the last dose received before the start of the event. For this summary, column headers will need to include all patients who were ever dosed at that dose level. Additionally, patients may be counted more than once for each event as the events will be tabled by the last dose level received on or prior to the start date of the event.

Listings of all TEAE, AE with outcome of death, SAEs, and AEs leading to discontinuation will be presented. A separate listing for non-treatment-emergent AEs will also be provided.

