#### 8.7.7. Concomitant Medications

Other than the study drug, any medication taken by patients during the course of the study with a start date or an end date on or after the first dose of the study drug, or marked as ongoing, will be considered concomitant. Medications stopped prior to the date of the first dose of study drug will not be considered concomitant. The number and percent of patients using each concomitant medication will be summarized according to the World Health Organization (WHO) Drug Dictionary preferred name. Patients with multiple uses of a concomitant medication during a treatment period will be counted once for a given preferred name for the treatment period. Additionally, prior and concomitant medication data will be listed.

Prior and concomitant corticosteroid use will be listed. Corticosteroids will be identified by an answer of "Yes" to the CRF question "Is medication a corticosteroid?".

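### An adverse event with a partial start date and a known pre-dose stop date is imputed to start after it stopped and is flagged treatment-emergent

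*SAP*

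**What the plan says.** SAP section 7.3 gives one set of date rules for AEs and concomitant medications. Three of its start-date rules return the first-dose date:

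- Day missing, month and year equal to those of first dose: "Otherwise, if the month and year are the same as first dose date, use first dose date".
- Day and month missing, year equal to that of first dose: "impute month and day with month and day of first dose date (assuming same 'year".
- Nothing recorded: "If the start date is completely missing, it will be set to the first dose date".

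None has a condition on the stop date. The section adds that listings show the recorded values and that "imputed dates will only be used for programming flags, etc".

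SAP section 8.7.2 gives three alternative routes to treatment-emergent status. The first is by timing: "AEs that occurred on or after the first dose of study drug and on or before the 30"th day after the last dose. The second is "AEs with a missing start date and a stop date on or after the first dose of study drug". The third covers events with neither date. The same section plans tables by the last dose level received on or before the event's start.

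SAP section 8.7.7 first counts a medication as concomitant if it starts or ends on or after first dose, or is ongoing. It then says: "Medications stopped prior to the date of the first dose of study drug will not be considered concomitant".

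**The concern.** Pre-dose AEs are expected in this database. The Protocol's summary of Amendment No. 2 records: "Change start time for collection of adverse events, serious adverse events, and pregnancies to the time of informed consent". Screening lasts up to 21 days, and SAP section 8.7.2 plans a separate listing of AEs that are not treatment-emergent. Medications reach back further: the summary of Amendment No. 3 sets the look-back for prior and concomitant medication at 30 days before screening.

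A screening-period AE can therefore have an uncertain start day and a known stop day before dosing. The stop date settles the matter, since the event was over before study drug was given. The rules in section 7.3 discard that information and give the event an onset on Day 1.

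The event then moves from the non-treatment-emergent listing into the treatment-emergent tables. In the by-last-dose tables, where an event that preceded every dose has no place, it is credited to the first dose level. AEs are part of the primary endpoint (SAP section 6.2), so the flag should follow from the rules without a programmer's judgement.

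**Working it through.** The plan states no figure to reproduce. The check applies the written rules to example records.

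**Inputs.** The start and stop rules come from SAP section 7.3, the treatment-emergent criteria from 8.7.2 and the concomitant rule from 8.7.7. Assumed for illustration: first dose 15 Mar 2015, last dose 15 Jun 2015, study end 10 Jul 2015. The treatment-emergent window then runs from 15 Mar to 15 Jun + 30 days = 15 Jul 2015. A stop date with only the day missing becomes the last day of its month.

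**Records that ended before first dose.**

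| Recorded start | Recorded stop | Imputed start | Stop used | Start minus stop | First criterion | Second criterion |
|---|---|---|---|---|---|---|
| day unknown, Mar 2015 | 10 Mar 2015 | 15 Mar | 10 Mar | 5 days | met | does not address partial starts |
| day and month unknown, 2015 | 10 Mar 2015 | 15 Mar | 10 Mar | 5 days | met | does not address partial starts |
| day and month unknown, 2015 | day unknown, Feb 2015 | 15 Mar | 28 Feb | 15 days | met | does not address partial starts |
| none | 10 Mar 2015 | 15 Mar | 10 Mar | 5 days | met | not met |
| none | day unknown, Feb 2015 | 15 Mar | 28 Feb | 15 days | met | not met |

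All five starts fall after the stop, which is impossible.

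- *Partial start (rows 1 to 3).* The first criterion is met on the imputed date, and nothing in 7.3 or 8.7.2 then looks at the stop. The AE is flagged treatment-emergent as the rules are written.
- *No start (rows 4 and 5).* The imputed date meets the first criterion, while the second, read on the recorded data, would leave the event out. The result depends on whether imputation comes before or after the test, which the SAP does not say.
- *The same records as medications.* In all five, the imputed start satisfies the inclusion sentence of 8.7.7 and the stop date satisfies its exclusion sentence. The two sentences disagree, and no precedence is stated.

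**Records that are handled correctly.** With a stop of 10 Mar 2015, a start with the day unknown in Feb 2015 becomes 1 Feb 2015, and one known only as 2014 becomes 1 Jan 2014. Both come out as not treatment-emergent and not concomitant. The fault is confined to starts that are moved to the first-dose date.

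**Effect of a cap.** Set start = min(imputed start, stop). In rows 1, 2 and 4 the start becomes 10 Mar 2015, and in rows 3 and 5 it becomes 28 Feb 2015. All five are then neither treatment-emergent nor concomitant. With a stop of 20 Mar 2015, min(15 Mar, 20 Mar) = 15 Mar, so the classification does not change.

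**Size of one misflagged patient.** The change in incidence is 1/n:

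- n = 10, the approximate Part 2 number per dose level (SAP section 4.1): 1/10 = 10 points.
- n = 6 or 3, an escalation cohort (SAP section 4.1.1): 1/6 = 17 points, 1/3 = 33 points.
- n = 30, if all three recommended-phase-2-dose cohorts of 10 are filled (SAP section 4.1): 1/30 = about 3 points, and less once the escalation patients at that dose are added.

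Each shift occurs only if the patient has no other treatment-emergent event in the same term.

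**The case against.** The strongest reply is that the second and third criteria of section 8.7.2 make sense only on recorded dates, because after imputation no start date would be missing. On that reading a fully absent start with a pre-dose stop is correctly left out. This is a fair reading, so for that case the fault is an unstated order of operations and not a certain misclassification. The reply does not reach partial starts. Section 7.3 distinguishes partial from completely missing dates, and the criteria in 8.7.2 do not mention partial ones. Stretching the second criterion to cover every incomplete start would make an event that began on an unknown day in an earlier month and ended after dosing treatment-emergent, whereas 7.3 dates it before first dose.

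It can also be said that an event which ended before dosing plainly did not occur after it. A careful programmer may see this, but the written rule directs that flags be set from the imputed date.

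For medications, the exclusion sentence of 8.7.7 depends only on the stop date and is the more specific of the two. A reader might infer that every such medication will be miscounted as concomitant. The documents do not support that: if the exclusion sentence is given precedence, none is. What remains is the conflict between the two sentences.

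A reader might also infer that an onset imputed to Day 1, inside the DLT Evaluation Period, could disturb DLT counts or the MTD. It does not. SAP section 8.7.1 says DLTs are flagged when AE data are collected, and the definition also requires Grade 3 or higher, onset after study drug, and no relation to underlying disease, intercurrent illness or concomitant medication. No imputed date creates a DLT.

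Finally, exposure is limited. An AE must begin after consent, end before dosing, and have a known stop but an uncertain start. Listings show the recorded dates, so affected records can be found.

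**Conclusion.** The point holds for AEs whose start lacks the day in the first-dose month, or the day and month in the first-dose year, and whose stop is known to precede first dose. As written, these get a start after their stop, are flagged treatment-emergent, and are credited to the first dose. For AEs with no start date, and for medications, the finding is narrower: two rules conflict and the SAP does not say which prevails.

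The point is minor. The documents do not give the number of such records; that it is small is an assumption, based on the short screening window. The 17 and 33 point shifts apply only to the smallest cohorts, with about 10 points in a Part 2 cohort and about 3 or less in a fully expanded one. The direction is over-counting, no event is hidden, and the AE summaries are descriptive. It is still worth correcting, because a stated rule produces impossible dates in a primary safety analysis.

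**What to change.** Add two sentences to SAP section 7.3:

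1. An imputed start date may not be later than the known or imputed stop date.
2. Any AE with a stop date before first dose is non-treatment-emergent, and any medication with a stop date before first dose is prior only, whatever the start date.

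The second sentence also settles the precedence left open in sections 8.7.2 and 8.7.7. Records with a stop on or after first dose keep their present classification. The cost is a short text change and about a line of code, with no new data.

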# 7.4. Interim Analyses and Data Monitoring

Not applicable.

#### 7.5. Multicenter Studies

There will be 4 to 8 investigative sites involved. The number and percentage of patients will be presented for each center. However, no other statistics will be presented by center and the data will be pooled together for the analysis.

# 8. STATISTICAL ANALYSIS

In this section and all after, when tables are presented by posttreatment visits, the last visit will be the visit at the end of study. When applicable, visits after the start of the maintenance phase and unscheduled visits will be included in a summary of maximum and minimum values observed for each patient's posttreatment visits, i.e., the minimum and maximum values are based on all the post treatment visits.

In general descriptive statistics for continuous variables will be summarized by the mean, standard deviation, 25th percentile, median (50th percentile), 75th percentile, minimum and maximum values. When continuous variables are displayed for less than 3 patients, only the number of observations will be presented. Categorical variables will be summarized using counts and percentages.

All raw data will be presented to the original number of decimal places. The means and medians will be presented to 1 more decimal place than the raw data. The standard deviations will be presented to 2 more decimal places than the raw data.

Baseline will generally be defined as data obtained as the last non-missing value prior to the first dose of study drug, i.e., including the pre-dose assessment on Day 1, assessments during screening and other assessments prior to the first dose of study drug.

AE tables and laboratory tables will be presented by visits and by tumor group. Tumor groups are defined as groups of overall, solid tumor, and AML patients.

Unless otherwise stated, summaries will be produced by dose cohort, which is defined as the intended and starting dose to which the patient was enrolled.

